- i. Data collection: The Data Manager will generate bi-weekly reports to check data quality, including completeness and out of range responses. The reports will be reviewed by the PIs and in-country staff will be responsible for resolving queries.
- ii. Study progress: The Steering Committee will review the research protocol and plans for safety and data monitoring and make recommendations for any changes to the PIs. The Data Manager will generate bi-weekly enrollment reports to track the progress of recruitment, enrollment, and retention. The PIs will review the reports and make changes as needed. The Steering Committee will also review quarterly reports on study progress, adverse events, breaches of confidentiality, AND unanticipated problems involving risk to participants or others. No interim safety or efficacy analyses are planned, as this is an implementation trial of an approved TB preventive therapy regimen.
- iii. Safety: Because this is an implementation trial, adverse events related to TB preventive therapy will be monitored as they would in routine practice/care. Briefly, for participants taking 3HP by DOT and attending weekly clinic visits, clinicians will administer a side effect screen, as per routine procedures. Participants taking 3HP by SAT will receive a weekly check-in via SMS or IVR phone call asking if they are well, with a follow up call from clinicians if necessary, to reflect standard screening procedures. Routine clinicians will make all decisions to interrupt or discontinue treatment and study staff will review patient charts to document reasons for interruption or discontinuation. As required by the Uganda National Drug (NDA) Authority, reasons for treatment interruption or discontinuation related to adverse events will be reported to the NDA. In addition, if any hospitalizations or deaths that clinicians suspect could be related to 3HP will be reported to the NDA and to the local and UCSF IRBs. Participant safety data will be part of the quarterly

reports sent to the Steering Committee, who will review reports and make recommendations to the PIs of any need to enhance safety monitoring plans beyond what would occur in routine care and/or to discontinue the study.

6. **Dissemination:** The trial results will be communicated to stakeholders through dissemination meetings and to participating health centers using language-appropriate information sheets. Investigators will present results at relevant conferences, and submit manuscript(s) to peer-reviewed journals. Public access to the participant-level dataset of main trial results and statistical code will be made available.

VII. Abbreviations

3HP	Three-month regimen weekly isoniazid and rifapentine
ART	Anti-retroviral therapy
CDC	Centers for Disease Control and Prevention
CHW	Community Health Worker
CI	Confidence Interval
CTCAE	Common Terminology Criteria for Adverse Events
DALY	Disability-Adjusted Life Year
DOT	Directly Observed Therapy
GCP	Good Clinical Practice
GNI	Gross National Income
IDI	In depth interviews
INH	Isoniazid
IRB	Institutional Review Board
IQR	Interquartile Range
IVR	Interactive Voice Response
KII	Key Informant Interviews
LTBI	Latent Tuberculosis Infection
MJAP	Makerere University Joint AIDS Program
NDA	National Drug Authority
NHLBI	National Heart, Lung, and Blood Institute
NIH	National Institutes of Health
NTLP	National Tuberculosis and Leprosy Program
PACTR	Pan African Clinical Trials Registry
PEPFAR	US President's Emergency Fund for AIDS Relief
PLHIV	People Living with HIV
REDCap	Research Electronic Data Capture
RPT	Rifapentine
SAT	Self-administered Therapy
SDM	Shared Decision Making
SMS	Short Message Service
TB	Tuberculosis
UCSF	University of California San Francisco
WHO	World Health Organization

VIII. References

1. Group TAS. A Trial of Early Antiretrovirals and Isoniazid Preventive Therapy in Africa. *N Engl J Med*. 2015.
4. Motsamai OI. *IPT Botswana Experience - Ministry of Health Botswana*.: World Health Organization: Meeting Presentation. Addis Ababa, Ethiopia.;2011.
5. WHO. *Report of a "lessons learnt" workshop on the six ProTEST pilot projects in Malawi, South Africa and Zambia*. Geneva, Switzerland: World Health Organization: Stop TB and HIV/AIDS Departments;2004.

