Participants randomized to the Patient Choice between facilitated DOT and facilitated SAT arm will be offered a choice between arms 1 and 2. A research nurse will review each section of the decision aid with participants, discuss values and preferences, and, after addressing any questions, ask participants to select facilitated DOT or facilitated SAT. Participants will have the option to switch between DOT and SAT at any time. The reason for switching and time spent under each strategy will be recorded.

Eligibility Criteria

To be included in the randomized trial, patients will have to meet all of the following inclusion criteria and none of the exclusion criteria:

1. Inclusion Criteria:

- a. HIV-positive client engaged in care at the Mulago ISS clinic
- b. Weight $\geq 40\text{kg}$
- c. Age 18 years or older
- d. Capacity to provide informed consent in English or Luganda

(From our experience conducting similar studies at the Mulago ISS clinic, the majority of patients receiving care at the clinic are able to communicate using the Luganda language. For example, while

conducting patient Knowledge, Attitudes and Practices (KAP) interviews during the formative phase, 21/25 (84%) participants opted for Luganda and only four of the 25 opted for English as the language for the interview. Therefore, in addition to Luganda, we selected English as the other preferred language for the study)

2. **Exclusion Criteria:**

- a. Suspicion of active TB based on positive WHO symptom screen AND elevated POC CRP, or current or planned TB treatment
- b. Actively taking an antiretroviral medication contraindicated for use with rifapentine under contemporary WHO or Ugandan policy
- c. Contact of a TB patient with known resistance to isoniazid or rifamycins
- d. Women who are pregnant, breast feeding or intending to get pregnant in the next 120 days. Note: women who become pregnant while on 3HP will be recommended to continue and complete 3HP treatment per Uganda 2020 Uganda National Guidelines, and will be monitored for side effects as per the study protocol ²⁶
- e. Prisoners
- f. Previously completed treatment for active TB or at least 6 months of isoniazid preventive therapy within past 2 years
- g. Not intending to remain within 25 km of the Mulago ISS clinic during the study period or to receive further care at the Mulago ISS clinic
- h. Lack of access to a mobile telephone or lack of willingness to receive SMS reminders/IVR phone calls

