- i. Pre-existing documentation of clinical liver disease.
- j. History of sensitivity or intolerance to isoniazid or rifamycins
- k. Another household member already enrolled in the study (household members cannot be effectively randomized to different arms)
- l. Actively taking medication contraindicated for use with rifamycin (e.g., warfarin, phenytoin)

Mixed methods and health economic sub-studies will include a subset of participants enrolled in the trial, as well as clinic administrators and clinicians (clinical officer, doctor, nurse, pharmacist, peer educators and counselors) involved in 3HP delivery at the Mulago ISS clinic.

Recruitment and eligibility screening

PLHIV will be recruited through Mulago ISS clinic providers, who will refer interested clients to study staff for eligibility screening, or directly from the patient waiting area by a trained research nurse. In order to be considered for study entry, all interested clients must have completed the following screening evaluations/documentation:

- A baseline medical history and clinical evaluation, including:
 1. Patient demographics (i.e., sex, age)
 2. Access to mobile telephone/willingness to receive SMS reminders/IVR phone calls
 3. Intention to remain within 25 km of the Mulago ISS clinic during the study period or to receive further care at the Mulago ISS clinic
 4. Height and weight
 5. Previous treatment for LTBI (i.e., if patient has previously completed a full course of 3HP or at least 6 months of isoniazid preventive therapy)
- Evaluation of contraindications for 3HP treatment, including:

1. Active treatment with an antiretroviral medication contraindicated for use with rifapentine under contemporary Ugandan policy
2. Current breastfeeding, pregnancy, or a plan to get pregnant within 120 days of enrollment (a pregnancy test in women of childbearing potential must be obtained \leq 14 days prior to enrollment).
Note: women who become pregnant while on 3HP will be recommended to continue and complete 3HP treatment per Uganda 2020 National Guidelines, and will be monitored for side effects as per the study protocol.
3. Contact of a case with known resistance to INH or rifapentine.
4. Risk for underlying liver disease which includes pre-existing documentation of clinical liver disease.

- Laboratory tests, including:
 1. A blood or urine pregnancy test done on all women of reproductive potential.
- Evaluation for active TB

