The primary outcome for our *cost-utility analysis* will be the incremental cost per DALY averted. We will calibrate a Markov model of long-term outcomes to a population of PLHIV in Uganda, simulating 10,000 PLHIV over time steps of six months. Markov states will include those relevant to TB preventive therapy (declined, partially completed, fully completed, and time since completion), TB (latently infected [including future infection], uninfected, active disease, treated), and HIV (ART status, viral suppression status, CD4 strata). We will estimate the incremental cost per DALY averted of patient choice relative to facilitated DOT or SAT. We will also incorporate the annual probability of first-order transmission (i.e., transmissions occurring from individuals eligible to receive preventive therapy who develop incident TB), as well as the (discounted) cost of diagnosing and treating those individuals with new active TB.^{29,30} We will adopt the societal perspective, with secondary analyses from the health system and patient perspectives. We will conduct one-way sensitivity analyses across all model parameters, multi-way sensitivity analyses for parameters found to be most influential, and a probabilistic uncertainty analysis in which all parameters are varied simultaneously using Latin Hypercube Sampling. Additional sensitivity analyses will include: (a) different assumptions about the duration of effectiveness of 3HP (including differential risks of reinfection)³¹ and (b) inclusion/exclusion of HIV-related costs (which tend to overshadow the costs of TB diagnosis and prevention).^{32,33}

4. **Adoption outcomes:** For each process metric, we will report the monthly proportion (95% Confidence Interval (**CI**)) or median (interquartile range (**IQR**)) to assess the implementation of intervention components in each arm overall and within sub-groups.
5. **Implementation outcomes:** Analysis of implementation outcomes will include multivariable regression models to compare by study arm patient survey data including a) patient costs; b) scores on questions related to patient barriers to TB preventative care; and c) patient satisfaction; and also to identify factors independently associated with 3HP completion across study arms.

Secondary analyses will include:

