[name] (statistician) will oversee data management in conjunction with UCSF- and Uganda-based study coordinators using the National Institutes of Health (**NIH**)-recommended Research Electronic Data Capture (**REDCap**) software, password-protected and accessible only to research staff. All data collection forms will be entered into REDCap, with validation of data using range and consistency checks. Quality control procedures will include review of all study data collection forms for completeness and accuracy prior to data capture. Queries performed on the database will be reviewed, verified and corrected on a twice-monthly basis. The UCSF study coordinator will visit Uganda 2-3 times a year and review a random sample of forms and primary data sources for quality assurance.

VI. Ethical Considerations

1. **Potential risks to participants:** The primary risk to participants is that of medication-induced adverse events (due to isoniazid or rifapentine), a risk that is greatly outweighed in this population by the potential benefit of prevented active TB among participants who complete treatment. 3HP is an approved treatment regimen for TB preventive therapy that has a lower rate of side effects than the most commonly used regimen (isoniazid daily for 9 months). In the PREVENT TB trial, major adverse events (Grade 3 or 4) occurred in 1.6% of patients.¹⁰ Overall, 4.9% of patients discontinued treatment due to adverse effects, including 2.9% due to hypersensitivity reactions. Hypersensitivity reactions may include a flulike syndrome (e.g., fever, chills, headaches, dizziness, musculoskeletal pain), thrombocytopenia, shortness of breath or other signs and symptoms including wheezing, acute bronchospasm, urticaria, petechiae, purpura, pruritus, conjunctivitis, angioedema, hypotension or shock. Other side effects, including hepatotoxicity, are uncommon with once-weekly dosing but will also be assessed at every clinic visit. Importantly, rifapentine given once weekly has also been shown to not have any negative effects on the efficacy of efavirenz-based ART regimens.

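### Exclusion (f) leaves out completed 3HP, so read literally a recent 3HP completer may enter for a second course while a recent isoniazid completer may not

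*Protocol*

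**What the plan says.** Entry is decided by the Eligibility Criteria in Protocol section IV: patients must "meet all of the following inclusion criteria and none of the exclusion criteria". Exclusion (f) is the only criterion on previously completed TB treatment or preventive therapy, and it reads "Previously completed treatment for active TB or at least 6 months of isoniazid preventive therapy within past 2 years".

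Recruitment and eligibility screening, in the same section, opens its list with "In order to be considered for study entry, all interested clients must have completed the following screening evaluations/documentation". Item 5 of the baseline history there is previous treatment for latent TB infection, explained as "if patient has previously completed a full course of 3HP or at least 6 months of isoniazid preventive therapy".

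Under Study Agents, everyone enrolled is to receive 3HP whatever their arm. Target Setting and Study Population notes that 3HP is a recommended regimen in Uganda.

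**The concern.** Screening treats a completed 3HP course and a completed isoniazid course as the same kind of history, but only the isoniazid course leads to exclusion. A person who recently finished the very regimen under study therefore remains eligible to take it again, and the protocol does not say why that person should be handled differently from a recent isoniazid completer.

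Two things are at stake. Some participants might be given a second course they do not need. Staff might also decide the same case differently: one nurse could see completed 3HP on the form and turn the client away, another could apply the written criteria and enrol, and the text supports only the second.

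**Working it through.** The check is a comparison of texts; the plan states no figure on this point to reproduce.

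**Step 1. Test case.** Take an adult who completed and tolerated 3HP within the past 2 years and who has no other reason for exclusion.

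**Step 2. Apply (f).**
- Active-TB limb: not met, because 3HP is preventive therapy.
- Isoniazid limb: not met. Protocol section II, Shorter LTBI Treatment Regimens, describes 3HP as a three-month, 12-dose regimen, separate from 6 to 9 months of daily isoniazid. Three months is less than six.
- The result is the same whether the 2-year window is read as covering both limbs or only isoniazid.

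**Step 3. Look for another rule.**
- (j) covers sensitivity or intolerance to isoniazid or rifamycins. Someone who tolerated the course passes it.
- (b) and (l) concern medicines being taken now, and (i) documented liver disease. None is triggered by a past 3HP course.
- The remaining criteria concern suspected or treated active TB, contact with resistant TB, pregnancy and breastfeeding, prison, location, telephone access and household members.
- The re-screening text adds no rule on prior 3HP. The SAP adds no eligibility rule or analysis exclusion for it.

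**Step 4. Result.**

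| History in past 2 years | Recorded under item 5 | Excluded by (f) | Excluded elsewhere |
|---|---|---|---|
| At least 6 months of isoniazid, completed | yes | yes | not needed |
| 3HP, completed and tolerated | yes | no | no |

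**Step 5. Scale.** The documents give no prevalence of prior 3HP, so the shares below are assumptions. People = share × 1656; further doses offered = people × 12.

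| Assumed share | People | Further doses |
|---|---|---|
| 0% | 0 | 0 |
| 0.5% | 0.005 × 1656 = 8.28 | 99 |
| 1% | 0.01 × 1656 = 16.56 | 199 |
| 2% | 0.02 × 1656 = 33.12 | 397 |

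**The case against.** The case against making much of this is fair in several respects.

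- **The lists do not contradict each other.** Item 5 sits under baseline medical history, not under the evaluation of contraindications. Recording a history is not a rule to exclude, and a criterion may be narrower than the history collected. This stands. A reader might also infer a proven drafting slip by pairing screening items with exclusions, but the pairing is loose both ways: height has no exclusion, and prisoner status has no screening item.
- **Timing.** A reader might infer that staff cannot apply the 2-year window because item 5 mentions no date. The screening form is not in the documents, and staff must establish timing to apply (f) at all. That inference is not supported.
- **Harm.** Protocol section VI reports for a previous trial that "4.9% of patients discontinued treatment due to adverse effects, including 2.9% due to hypersensitivity reactions". Applying those rates to the 2% row gives 33.12 × 0.049 = 1.6 discontinuations, of which 33.12 × 0.029 = 1.0 for hypersensitivity. That is not a usable estimate. The share is assumed, the rates are not for a second course, and the people concerned finished a first course and passed (j).
- **Re-treatment may be reasonable.** The cost-utility analysis plans sensitivity analyses over "different assumptions about the duration of effectiveness of 3HP (including differential risks of reinfection", so the duration of protection is treated as uncertain. Someone who completed isoniazid more than 2 years ago is already eligible. The documents therefore do not show that a second course is useless. They still leave unexplained why recent 3HP and recent isoniazid are handled differently, and the risk-benefit statement in section VI does not address an early repeat of the same regimen.
- **Calendar.** Table 1 places enrollment and follow-up in 2020 and 2021, and SAP section 2.3 cites a protocol version of May 2022. On that schedule a rewording would come after enrollment. The documents do not give the actual closing date.

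None of this supplies a rule that excludes a recent 3HP completer.

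**Conclusion.** The point holds, as a minor one. As written, (f) admits a person who completed and tolerated 3HP within the past 2 years and offers a second 12-dose course, while it turns away a person who completed isoniazid in the same period. No other criterion changes that.

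The size is unknown and may be zero. The range of 0 to about 33 people rests wholly on assumed shares of 0% to 2%. The benefit of correcting it is limited to avoiding unneeded re-treatment and making eligibility decisions consistent.

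A reader might go further and infer bias in the comparison of arms, or in the test against the 80% target. The documents do not support that: eligibility is settled before randomization, which should spread any such clients across the three arms, and nothing shows how prior 3HP would shift completion. No power, alpha or analysis figure is affected.

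**What to change.** Reword (f) to list three completed treatments under one 2-year window: treatment for active TB, at least 6 months of isoniazid preventive therapy, or a full course of 3HP. The 2-year window for 3HP is taken over from the isoniazid limb, because the documents give no separate basis for one.

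The cost is a minor protocol amendment, with the ethics review that goes with it, and possibly a few fewer eligible clients. No visit, sample size or analysis changes. The rewording affects who is enrolled only while recruitment is open.
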